Table 1 Changes to Protocol Defined Analysis Plan	16

VERSION HISTORY

SAP Version	Approval Date	Protocol Version (Date) on which SAP is Based	Change	Rationale
SAP	06 Dec 2022	08-Jul-22	Not Applicable	Original version
Amendment 01	16 Aug 2023	28-Nov-22	Section 6.2.1 updated	Discrepancy between PCI ranges and units provided in SAP and values collected by lab
			Removed wording which mentioned PEF data would be summarised.	PEF is being collected for monitoring purposes only and is not recorded in the eCRF.

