4.2.1. Definition of endpoints

Adverse events will be coded using the latest standard Medical Dictionary for Regulatory Affairs (MedDRA dictionary).

Grade 1 AEs are defined as mild. Grade 2 or higher AEs are defined as moderate or severe. This study will report AEs as mild, moderate, or severe.

CONFIDENTIAL

A study intervention-related AE/SAE is defined as an AE/SAE for which the investigator classifies the possible relationship to study intervention as “Yes”. A worst-case scenario approach will be taken to handle missing relatedness data, i.e., the summary table will include events with the relationship to study intervention as ‘Yes’ or missing.

Spirometry assessments are performed in triplicate with the highest value reported.

Whilst all data collected will be summarized, only measurements which are clinically significant at any timepoint between randomization and follow up will be reported as part of the primary endpoint.

Clinically significant values are defined as:

- Values in the potential clinical interest (PCI) ranges for laboratory values, vital signs, ECGs and spirometry.
- Values that achieve the study stopping criteria (protocol Section 7.1.3) for spirometry

The PCI ranges will be defined in the Section [6.2.1](#).

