4.2.2.2. Laboratory Data, Vital Signs, ECGs

For haematology, clinical chemistry, urinalysis, vital signs, ECG and spirometry data the following information will be summarised:

- 1) Clinically significant values at each visit
- 2) Raw and change from baseline values at each visit

Note: The first table is the only one included as part of the primary endpoint. Urinalysis data is only collected when there is an abnormal finding and so it is expected that urinalysis tables/listings will be sparse.

Laboratory Data

For laboratory data, separate tables for haematology, clinical chemistry and urinalysis tests will be produced. Laboratory evaluations including the analyses of Clinical chemistry tests, haematology tests and urinalysis, will be based on GSK Core Data Standards. Liver biochemical parameters will be included with clinical chemistry tests.

The details of the planned displays will be given in the OPS. Incidence of clinically significant laboratory parameters will be reported.

Vital Signs

The analyses of vital signs will be based on GSK Core Data Standards, unless otherwise specified.

In vital sign assessment, pulse rate, respiratory rate, tympanic temperature, and systolic and diastolic blood pressure will be assessed. Blood pressure and pulse measurement will be taken in the semi supine position.

Incidence of clinically significant vital sign parameters will be reported. Refer the normal ranges of laboratory parameters in the Section [6.2.1](#)

Further details of the planned displays will be given in OPS.

ECG

The QTc data analysis will use the collected values based on Fridericia formula.

The analysis of 12-lead ECG along with any ECG findings will be reported according to GSK Core Data Standards.

Safety ECGs will be performed in semi-supine position after at least 5 minutes rest. The parameters collected are PR, QRS, QT and QTc intervals.

Incidence of clinically significant ECG parameters will be reported. Refer the normal ranges of laboratory parameters in the Section [6.2.1](#)

Further details of the planned displays will be given in OPS.

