5. SAMPLE SIZE DETERMINATION

No formal statistical techniques were used to calculate the sample size for this study.

The number of participants included is deemed an adequate number to provide an assessment of safety and tolerability and pharmacokinetics measurements.

Sufficient participants with COPD will be screened and randomized to receive GSK3923868 or placebo in a 3:1 ratio with the intention of a minimum of 8 and a maximum of 12 participants to complete the study.

In total, up to 9 participants are planned to receive each dose of active drug in each period. If the true adverse outcome rate is 5%, the chance of observing at least one adverse event at a given dose is 37%. If the true adverse outcome rate is 20%, the chance of observing at least one adverse event at a given dose level is 87%. For sample size of 6 participants on active drug in each period, if the true adverse outcome rate is 5%, the chance of observing at least one adverse event at a given dose is 27%. If the true adverse outcome rate is 20%, the chance of observing at least one adverse event at a given dose level is 74%.

This level of predictivity is deemed adequate within this phase of development.

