6.2. Appendix 2 Data Derivations Rule

6.2.1. Criteria for Potential Clinical Importance

- **Laboratory Values**

Haematology				
Laboratory Parameter	Units	Category	Clinical Concern Range	
			Low Flag (<x)	High Flag (>x)
Platelet Count	10 ⁹ /L		31	900
RBC Count	10 ¹² /L		4.2	5.9
Hemoglobin	g/L	Male	90	180
		Female	90	180
Hematocrit	fraction of 1			1.5*ULN
RBC Indices				
MCV	fL		0.75*LLN	1.5*ULN
MCH	pg		28	32
%Reticulocytes	%		na	2*ULN
WBC Count with differentials				
Lymphocytes	10 ⁹ /L		0.6	6
Neutrophil Count	10 ⁹ /L		1.5	12
Monocytes	10 ⁹ /L		na	2
Eosinophils	10 ⁹ /L		na	0.5
Basophils	10 ⁹ /L		na	2*ULN

CONFIDENTIAL

Clinical Chemistry				
Laboratory Parameter	Units	Category	Clinical Concern Range	
			Low Flag (<x)	High Flag (>x)
Albumin	g/L		32	50
Calcium	mmol/L		2.2	3.24
Creatinine	umol/L	Male 40-49 years	69	106
		Male 50-59 years	67.2	106
		Male 60-69 years	67.2	106
		Male 70+ years	59.2	106
		Female 40-49 years	52.2	106
		Female 50-59 years	53	106
		Female 60-69 years	53	106
		Female 70+ years	55.7	106
Glucose	mmol/L		4.0	7.8
BUN	mmol/L		2.5	15
Potassium	mmol/L		3.5	5.2
Sodium	mmol/L		136	145

CONFIDENTIAL

Liver Function			
Test Analyte	Units	Category	Clinical Concern Range
Alanine Aminotransferase (ALT) / Serum Glutamic-Pyruvic Transaminase (SGPT)	U/L	High	≥2x ULN
Aspartate Aminotransferase (AST) / Serum Glutamic-Oxaloacetic Transaminase (SGOT)	U/L	High	≥2x ULN
Alkaline phosphatase	U/L	High	≥2x ULN
T Bilirubin	μmol/L	High	≥ 1.5x ULN
Direct Bilirubin	μmol/L		0 – 6

- **ECG**

ECG Parameters	Unit	Clinical Concern range	
		Lower(<x)	Upper(>x)
Absolute			
Absolute QTc Interval	msec		> 600
Absolute PR Interval	msec	< 85	> 240
Absolute QRS Interval	msec	< 70	> 120
Change from Baseline			
Increase from Baseline QTc	msec		> 60

- **Vital Signs**

Vital Parameters (Absolute)	Unit	Clinical Concern range	
		Lower(<x)	Upper(>x)
Heart rate	bpm	35	110
Respiratory Rate	breaths/pm	8	20
Systolic blood pressure	mmHg	95	160
Diastolic Blood Pressure	mmHg	55	100
Temperature	°C	35.6	37.7

- **Spirometry**

Any participant experiencing a reduction in FEV1 at the 1-hour post-dose compared to daily pre-dose value of > 20%.

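### SAP 6.2.1 sets red-cell limits on different severity scales, so any haemoglobin from 90 to below 117.6 g/L is flagged through RBC count or MCH although the haemoglobin row does not flag it

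*SAP*

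**What the plan says.** SAP 4.2.1 treats as clinically significant any "Values in the potential clinical interest (PCI) ranges for laboratory values, vital signs, ECGs and spirometry". It adds that "only measurements which are clinically significant at any timepoint between randomization and follow up will be reported as part of the primary endpoint". SAP 4.2.2.2 plans two laboratory summaries, one of clinically significant values and one of raw and change-from-baseline values, and notes that "The first table is the only one included as part of the primary endpoint". Neither section requires a change from baseline or an investigator's judgement before a value counts.

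The limits are in the haematology table of SAP 6.2.1:

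- RBC count: flagged below 4.2 or above 5.9 x10^12/L, one range for both sexes.
- MCH: flagged below 28 or above 32 pg.
- Haemoglobin: "Hemoglobin g/L Male 90 180", with the same limits for females.
- MCV: "MCV fL 0.75*LLN 1.5*ULN", that is, multiples of laboratory limits that the documents do not give.

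The SAP gives no reason for using different degrees of severity. The version history explains the last change to this section only as "Discrepancy between PCI ranges and units provided in SAP and values collected by lab". The vital-sign and ECG paragraphs of SAP 4.2.2.2 also describe the section loosely: "Refer the normal ranges of laboratory parameters in the Section" 6.2.1. That leaves it unclear whether the limits are meant as normal ranges or as thresholds of concern.

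**The concern.** RBC count, MCH and haemoglobin are tied by definition, so their limits can be checked against one another. If the RBC and MCH windows are much tighter than the haemoglobin window, the same blood sample is clinically significant on one row and not on another, and the SAP does not say which is intended.

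The study tests no hypothesis. Readers will judge laboratory safety from these counts, in small columns: "In total, up to 9 participants are planned to receive each dose of active drug in each period". A count raised by two tight rows would label as clinically significant red-cell values that the SAP's own haemoglobin criterion passes. Without a baseline condition, a participant whose MCH is habitually just outside 28 to 32 pg would be reported at draw after draw. The endpoint itself, as worded in SAP 1.1, concerns changes.

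**Working it through.** **The plan's own figures.** The SAP states no flag rate for these limits. Its only related figures are the chances of at least one event in SAP 5, from 1 - (1 - p)^n:

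- n = 9: 36.98% at p = 5% and 86.58% at p = 20% (stated 37% and 87%).
- n = 6: 26.49% and 73.79% (stated 27% and 74%).

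These reproduce to within one percentage point. The same formula is used below.

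**Step 1: the identity.** Haemoglobin (g/L) = RBC (10^12/L) x MCH (pg). This follows from the definition of MCH and the units in SAP 6.2.1.

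**Step 2: low end.** The lowest haemoglobin with neither RBC nor MCH flagged is 4.2 x 28 = 117.6 g/L. The haemoglobin row flags below 90 g/L. Samples from 90 to below 117.6 g/L therefore pass the haemoglobin row but must fail RBC or MCH. That span is 117.6 - 90 = 27.6 g/L, or 27.6/90 = 31% of the 90 to 180 window.

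Example at 100 g/L: with MCH 30, RBC is 100/30 = 3.33, which is flagged; with RBC 4.2, MCH is 100/4.2 = 23.8, which is flagged. At exactly 90 g/L, RBC would be 2.81 to 3.21 if MCH were 28 to 32, or MCH would be 15.3 to 21.4 if RBC were 4.2 to 5.9.

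**Step 3: high end.** The highest haemoglobin with neither flagged is 5.9 x 32 = 188.8 g/L, above the limit of 180. RBC above 5.9 can still be flagged while haemoglobin is not, but no haemoglobin from 117.6 to 180 g/L forces a flag.

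**Step 4: width of each window (high limit / low limit).**

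- MCH: 32/28 = 1.14
- RBC: 5.9/4.2 = 1.40
- Haemoglobin: 180/90 = 2.00
- MCV: at least 1.5/0.75 = 2.00, multiplied further by ULN/LLN

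At a constant haemoglobin concentration per cell, MCH and MCV move in proportion. The MCH window spans about 14% and the MCV window at least a factor of two. This is a difference of scale, not a logical conflict, because LLN and ULN are not given.

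**Step 5: how often (assumed).** The documents give no MCH distribution. Take a normal distribution with mean 30 pg, so that p = P(|MCH - 30| > 2):

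| SD (pg) | p | Expected among 12 | At least one among 9 |
|---|---|---|---|
| 1.0 | 4.6% | 0.5 | 34% |
| 1.5 | 18.2% | 2.2 | 84% |
| 2.0 | 31.7% | 3.8 | 97% |

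A mean other than 30 raises p at a given SD. These are illustrations for MCH alone.

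**The case against.** Limits for different analytes need not be equally severe, and the consequences are bounded in several ways.

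- **The haemoglobin row stays visible.** A reader might infer that a true fall in haemoglobin would be lost among RBC and MCH flags, or that the haemoglobin limit is redundant because anything below 90 g/L is already flagged elsewhere. The documents do not support this. Haemoglobin has its own row in SAP 6.2.1, and SAP 4.2.2.2 reports incidence for laboratory parameters. Redundancy would matter only for a combined red-cell count, which neither document defines. Display details are left to the output specification, which is not available here.
- **The flags are not a false drug signal.** Each period has 9 active and 3 placebo participants, but Table 1 in protocol 4.1 takes the same 12 people through all three periods, and 9 of them receive placebo once. Many habitual flags would recur on active and placebo, and the change-from-baseline summary would show them as stable. The chance of at least one flag is not the chance of a misleading treatment difference.
- **A baseline condition would remove most persistent flags.** It would not remedy the mismatch between rows: a haemoglobin that falls during the study to between 90 and 117.6 g/L would still be flagged on one row and passed on another.
- **There is a second safeguard.** Protocol 8.2.5 has the investigator judge laboratory changes and record clinically significant ones as adverse events, independently of these limits.
- **Other rows are narrow too.** Sodium at 136 to 145 mmol/L is one, so correcting two rows will not clear the whole table.

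All of this stands and limits the size of the point. None of it explains why one table should pass and flag the same sample.

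**Conclusion.** The inconsistency is real and follows from the SAP's own limits: any haemoglobin from 90 to below 117.6 g/L is clinically significant through RBC count or MCH and not through haemoglobin. SAP 4.2.1 and 4.2.2.2 carry those flags into the primary-endpoint laboratory table. The conflict is forced only at the low end, and the contrast with MCV is one of scale.

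The effect is inflated RBC and MCH rows, and an inflated overall haematology count if one is produced, on both active and placebo. No hypothesis test is affected. The 5% to 32% range for MCH flags rests entirely on the assumed normal distribution with mean 30 pg and SD 1.0 to 2.0 pg; the 117.6 g/L figure needs no such assumption. The point deserves correction as a labelling fault in the primary endpoint, not as a threat to the study's safety conclusions.

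**What to change.** In SAP 6.2.1, remove RBC count and MCH from the table of limits, keep both in the raw and change-from-baseline summaries, and let haemoglobin carry the red-cell criterion.

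Alternatively, keep the two rows but reset their limits to the severity of the haemoglobin row. Check that the product of the two low limits comes to about 90 g/L and the product of the two high limits to about 180 g/L. Copying the MCV rule would not do this: if 5.9 were taken as the ULN (an assumption), the upper RBC flag would move to 1.5 x 5.9 = 8.85, which at MCH 28 means haemoglobin of 247.8 g/L, so the flag would be nearly inert.

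In SAP 4.2.1, count a flag only if the value was not already in the flagged range at the baseline defined in SAP 4.1.2. This matches the endpoint's reference to changes.

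The cost is SAP wording and a programming change, with no new data. The downside of removing the rows is that isolated shifts in RBC count or MCH would be seen only in the descriptive summaries.

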1.3.2. Single Ascending Dose (Treatment Periods 1 and 2)

Procedure	D-1	Treatment Periods 1 and 2										D2	D3
		Pre-dose	0h	5m	15m	30m	45m	1h	2h	4h	6h		
Site Visit	X							X					
Site Overnight Stay ¹	X							X					
Discharge from Site												X	
Phone Call													X
Review Inclusion and Exclusion Criteria	X												
Alcohol Urine Test	X												
Urine Drug Screen	X												
COVID-19 Testing ²	X												
Brief Physical Examination	X												
Inhaler Training (refresher) ³	X												
Randomisation (Period 1 only)		X											
Treatment Administration ⁴			X										
AE Review (include washout)				←								→	
SAE Review (include washout)			←									→	
Conmed Review			←									→	
Spirometry (FEV1)		X						X				X	
Vital Signs ⁵		X					X					X	X
12-Lead Safety ECG (single)		X						X				X	
Laboratory Safety Assessment ⁶	X											X	
Urinalysis	X												
Urine Pregnancy Test	X												
PK Blood Sample		X		X	X	X	X	X	X	X	X		
Genetic sample ⁷ (optional)		X											

1. Day -1 site admission would be optional.
2. To be performed according to local site policy on Day -1.
3. To be provided before first dose administration. If necessary, another inhaler refresher training may be provided in treatment period
4. Participants should fast for at least 6 hours before dosing until 1 hour post-dose. No water from 1 hour before dosing until 1 hour post-dose. See Section 5.3 for details.
5. Includes systolic and diastolic blood pressure, heart rate, respiration rate and tympanic temperature. Tympanic temperature will be measured once per day in the morning only.
6. Clinical chemistry and hematology only.
7. Genetic sampling can be conducted at any onsite visit during the study.

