4.2. Primary Endpoint(s) Analyses

All safety analyses will be performed on the Safety Analysis set, unless otherwise specified.

Primary Endpoints:

- Adverse events (AEs) and serious adverse events (SAEs).
- Clinically significant changes in laboratory values, vital signs, 12-lead ECG, and spirometry measurements up to Follow Up.

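### For laboratory values, vital signs and absolute ECG intervals, the primary endpoint of clinically significant changes is counted from absolute values with no baseline condition, so unchanged pre-dose abnormalities can enter the only primary table

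*SAP*

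**What the plan says.** SAP 4.2, in line with Protocol 3, names the second primary endpoint as "Clinically significant changes in laboratory values, vital signs, 12-lead ECG, and spirometry measurements up to Follow Up". SAP 4.2.1 then defines clinical significance by level: "Values in the potential clinical interest (PCI) ranges for laboratory values, vital signs, ECGs and spirometry", with the Protocol 7.1.3 stopping rule added for spirometry. On timing it states that "only measurements which are clinically significant at any timepoint between randomization and follow up will be reported as part of the primary endpoint".

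SAP 4.2.2.2 plans two summaries of these data: "Clinically significant values at each visit" and "Raw and change from baseline values at each visit". It adds that "The first table is the only one included as part of the primary endpoint".

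Three other sections bear on the point:

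- SAP 6.2.1 lists the PCI limits. Most are absolute.
- SAP 4.1.2 sets one study baseline, the last value before the first dose.
- SAP 6.2.2 separates pre-intervention from on-intervention time. SAP 4.2.1 does not refer to that split and uses its own window, which opens at randomisation.

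**The concern.** A change needs a reference point, and a value in a range has none. A participant who enters with a value beyond a PCI limit and stays there meets the SAP 4.2.1 definition at every visit where the parameter is measured, on active or on placebo, although nothing has changed. Entry does not screen such people out in general: Protocol 5.2 permits adequately treated, well-controlled concurrent conditions and sets few numerical limits on laboratory values or vital signs.

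The AE half of the primary endpoint works the other way. SAP 4.2.2.1 bases AE summaries on events with onset on or after the start of study intervention, and Protocol 8.3.1 records non-serious occurrences between consent and first dose as medical history. The PCI counts have no matching rule.

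What is at stake is how the primary table reads in a very small trial. A count in a dose column could be a new finding or a standing one, and the definition does not separate them.

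**Working it through.** **1. Which criteria ignore baseline (SAP 6.2.1).**

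| Group | Absolute | Change-based |
|---|---|---|
| Haematology | 12 | 0 |
| Clinical chemistry | 7 | 0 |
| Liver function | 5 | 0 |
| Vital signs | 5 | 0 |
| ECG | 3 (QTc, PR, QRS) | 1 (QTc increase > 60 msec) |
| Spirometry | 0 | 1 (FEV1 fall > 20% from daily pre-dose) |
| Total | 32 | 2 |

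So 32 of 34 criteria carry no baseline condition. One of the 32, absolute QTc > 600 msec, is largely shielded because Protocol 5.2 excludes QTcF > 450 msec at screening.

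**2. What falls in the window before dosing.** Protocol 1.3.2 places randomisation in the pre-dose column of Period 1. Vital signs and ECG are scheduled in that same column, so those pre-dose readings can fall inside the window. Period 1 safety laboratory samples are on Day -1 and precede it. For laboratory values in Period 1, the issue is therefore the later samples that repeat a standing abnormality, not the pre-dose sample itself.

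**3. The plan's own figures (SAP 5, Protocol 9.2).** The chance of at least one event among n participants at rate p is 1 - (1 - p)^n.

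- n = 9: 1 - 0.95^9 = 37.0% (stated 37%); 1 - 0.80^9 = 86.6% (stated 87%).
- n = 6: 1 - 0.95^6 = 26.5% (stated 27%); 1 - 0.80^6 = 73.8% (stated 74%).

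These reproduce, apart from a trivial rounding difference in the third.

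**4. The same formula applied to standing abnormalities.** The documents give no share of participants already in a PCI range, so q is an assumption, for one parameter at a time. With no drug effect, the chance of at least one counted participant on active under the present definition is:

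| Assumed q | n = 9 | n = 6 |
|---|---|---|
| 2% | 16.6% | 11.4% |
| 5% | 37.0% | 26.5% |
| 10% | 61.3% | 46.9% |
| 20% | 86.6% | 73.8% |

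If only values absent at baseline counted, each entry would be zero. At q = 5% the expected number is 9 x 0.05 = 0.45 participants.

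Now add an assumed true emergent rate of 5%, independent of baseline status, with n = 9:

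- Present definition, 1 - [(1 - q) x 0.95]^9: 60.3% at q = 5%, 75.6% at q = 10%.
- New values only, 1 - [1 - (1 - q) x 0.05]^9: 35.5% and 33.9%.

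**5. Size of one participant.** 1/9 = 11.1 percentage points in the affected parameter's row.

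**6. Direction.** Protocol Table 1 has four sequences of three participants: APA, AAP, AAA and PAA. Three of the four contain both treatments, so 9 of 12 participants receive both. Three receive active throughout, and a standing abnormality in one of them would appear in three active columns and never under placebo. Because sequences are randomised, the expected share with a standing abnormality is q on active and q on placebo in every period.

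**The case against.** The strongest reply is that treatment-emergent change is already covered. Protocol 8.2.5 has the investigator record clinically significant laboratory changes as AEs, Protocol 10.3.1 brings in other safety results that worsen from baseline, and AE summaries are limited to emergent events. The PCI table is by visit, so timing stays visible. Change from baseline is tabulated separately, SAP 6.2.2 classes pre-dose readings as pre-intervention, and no hypothesis is tested. The OPS and the sponsor's data standards, which fix the displays, are not available here and might show baseline status.

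Most of this stands, and it limits the consequence. It does not close the gap. The AE route depends on investigator judgement and is a separate endpoint. SAP 4.2.2.2 places the change table outside the primary endpoint. SAP 6.2.2 is not applied to the PCI counts, and it would not remove an on-treatment value that merely repeats baseline.

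Several stronger readings are tempting but not supported:

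- *That the whole endpoint ignores baseline.* FEV1 and QTc increase are change-based.
- *That standing abnormalities will be reported as drug effects, or will hide or mimic a signal.* The text fails to prevent their being counted. It does not label them as drug effects, and the crossover makes them mainly background.
- *That a large share of participants will carry at least one baseline flag.* Multiplying assumed rates across parameters describes an any-parameter composite that the SAP does not plan. Prevalence and independence would both be invented.
- *That the limits themselves prove many flags.* Haemoglobin is flagged only below 90 g/L, yet haemoglobin equals RBC count times MCH, so a value below 4.2 x 28 = 117.6 g/L must trip the RBC or MCH limit. That shows uneven strictness, which is a separate question of threshold choice. It says nothing about frequency.

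**Conclusion.** The endpoint's wording and its operational definition disagree for laboratory values, vital signs and absolute ECG intervals. Followed as written, the SAP allows values already in a PCI range before the first dose, and unchanged since, to count in the only primary table for these data. For pre-dose readings in Period 1, this reaches vital signs and ECG only.

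The size is 11 percentage points per affected participant in that parameter's row, with 9 on active. The frequency is unknown. The probabilities above rest on assumed values of q and an assumed 5% emergent rate, and serve only to show that a count cannot separate the two sources: a 5% standing prevalence and a true 5% adverse outcome rate both give 37%. The harm is blurred interpretation, not systematic bias towards either treatment. The change is worth making because it alters the primary counts and uses data already collected.

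**What to change.** In SAP 4.2.1, for the absolute criteria, define the primary count as values after the first dose that lie in the PCI range where the SAP 4.1.2 study baseline either was not in the range, or was in it and the value has moved further out in the same direction. Apply the SAP 6.2.2 pre-/on-intervention classification to these counts. Leave the QTc-increase and FEV1 criteria as they are. Add a supporting table with baseline PCI status and the all-values PCI counts. State how a missing baseline is handled, since SAP 4.1.2 leaves it missing.

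The study baseline is preferable to a fresh baseline in each period. A period baseline would depart from SAP 4.1.2. It would also absorb an abnormality that arose on an earlier active dose and persisted to the next pre-dose sample. The price is that a persistent new abnormality counts again in later periods, possibly under a different treatment; the by-visit layout shows this.

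The cost is SAP wording and slightly more programming. A participant already in range at baseline counts in the primary table only if worse, which the supporting table covers.
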